5. TREATMENT OF SUBJECTS

5.1 Diagnostic work-up before inclusion

The goal of the diagnostic work-up is to characterize the cyst and to rule out malignancy. This work-up should have taken place no more than 6 months prior to inclusion. A high quality cross-sectional imaging study, either Computed Tomography (CT) or Magnetic Resonance Imaging (MRCP) should always be performed. (based on the consensus statement, MRCP is preferred). In addition, in new cysts (diagnosed less than 6 months prior to inclusion), serum CA 19.9 should be determined. New cysts over 1 cm in size should also be evaluated by endoscopic ultrasonography (EUS), with fine needle aspiration (FNA), if technically feasible.

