6.1.2 Secondary study endpoints

- The outcome of patients with an indication for cyst resection (treated and non-treated), in terms of the number of operated patients, surgical procedures, morbidity, mortality, and cyst recurrence (Table II and III).
- Cyst evolution, in terms of development of symptoms, cyst growth, nodules, and secondary pancreatic duct dilatation.
- The perceived burden of surveillance for participants, as assessed by questionnaires regarding attitude towards surveillance and general anxiety and depression (Hospital Anxiety and Depression scale, HADS) (Table V) [15-19].

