The pathology department will handle the cyst fluid; at least 0.5 ml is centrifuged to generate deposit and supernatant fluid. The deposit will be used to process a smear and/or cellblock, for pathological analysis. The supernatant fluid will be sent out to the laboratory for biochemical analysis (CEA, CA 19.9, amylase). If at least 0.5 ml of the cyst fluid is left after the above mentioned procedures, this should be stored and frozen at

minus 80 degrees Celsius, for future molecular analysis. This step will be omitted in centers without such freezing facilities.

The pathologist will be provided with a protocol regarding the aspects that need to be addressed in the pathology report. On request, the pathologist of the investigators team (KB) can be consulted for advice or a second opinion. If surgery is performed, a glass slide of the pathological specimen (or a histological sample, preserved in formalin) must be sent to the pathology department of the Erasmus Medical Center in Rotterdam, for revision.

Laboratory investigations

To determine the serum CA 19.9 level, a blood sample of at least 6 ml must be collected. For each hospital, the local laboratory technique and cut-off value for CA 19.9 will be applied and recorded. In addition, for future genetic testing, two additional 6 ml blood samples will be drawn (one EDTA, one Serum tube) and stored at –20 and -80 degrees Celsius, respectively. This only applies for participating centers with such facilities.

Collection and storage of samples

All human samples that are collected during the study will be stored locally. If local facilities are not sufficient, samples may be sent to the Erasmus University Medical Center Rotterdam, for storage.

Patient questionnaires

Patients with a newly diagnosed cyst will be asked to fill out a questionnaire at home (Table V). This questionnaire will be sent to them by email (if they gave permission to do so) at study entry, after every follow up visit for the first three years, once after 5 and 10 years, and after cyst related events. The questionnaire can be filled out on-line, which will take approximately 5 to 15 minutes. Patients who fail to respond to the questionnaire will be reminded by email after two weeks. Patients who do not want to provide their email address will be able to join the study, without participating in the questionnaire evaluation.

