8.3 Multivariate analysis

Multivariate survival analysis will only be performed if the number of events will be > 30 . This is expected to be the case for the primary endpoint. The potential risk factors, given above, will have first interest. A statistical program (MPlus) will be used to perform multilevel analysis of longitudinal data (repeated measures), to analyze changes over time for the different patient reported outcomes, such as cancer worries, anxiety, and depression[20].

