Insulin use	Pancreatic duct communication (Y/N)	
Smoking	Main pancreatic duct dilatation (Y/N)	
Alcohol abuse	Common bile duct dilatation (Y/N)	
	Calibre change main PD (Y/N)	
Serum CA 19.9 level		

Table V: Patient Questionnaire

I. History and background (to evaluate risk factors)
 
Height and weight
 
Smoking and drinking habits
 
History of pancreatitis, pancreatic cysts/cancer/surgery, Diabetes, and insulin use
 
Family history of pancreatitis, and breast/colon or pancreatic cancer

II. Worries and burden of investigational procedures
 
Burden of imaging (MRCP/EUS/CT)

III. Questions regarding the general burden of surveillance and cancer worries
 
Regular checking of a pancreatic cyst...
 
 - Is a good way to detect cancer in time. - Lessens my fear to get cancer. - Gives me a sense of security. - Can lead to unnecessary uncertainty. - Is not important to me, since it will be too late to change the outcome of the disease anyway 
To what extent...
 
 - Do you find the check-ups burdensome? - Do the advantages of the check-up outweigh the disadvantages for you? - Are you nervous when you have to come for your check-up visit? - Do you dread the next check-up visit? 
How often would you like to have your pancreatic cyst checked?
 
For how long would you like to be checked?
 
Did the cyst surveillance change the extent to which you worry about cancer?

IV. Hospital Anxiety and Depression Scale
 
I feel tense or wound up.
 
I still enjoy the things I used to enjoy.
 
I get a sort of frightened feeling, as if something bad is about to happen.
 
I can laugh and see the funny side of things.
 
Worrying thoughts go through my mine.
 
I feel cheerful.

I can sit at ease and feel relaxed.

I feel as if I am slowed-down.

I get a sort of frightened feeling, like butterflies in my stomach.

I have lost interest in my appearance.

I feel restless and have to be on the move.

I look forward with enjoyment to things.

I get sudden feelings of panic.

I can enjoy reading a good book or watching a radio or TV programme.

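### Section 8.3 plans to model change over time in cancer worries, but no printed item in Table V measures the current level of cancer worry

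*Protocol*

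**What the plan says.** The primary objective (section 2) includes the burden that participants perceive. Section 6.1.2 makes this a secondary endpoint: "The perceived burden of surveillance for participants, as assessed by questionnaires" on attitude towards surveillance, together with the HADS.

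Under the patient questionnaires heading of section 6.3, the Table V questionnaire goes to patients with a newly diagnosed cyst, "at study entry, after every follow up visit for the first three years, once after 5 and 10 years, and after cyst related events". No separate entry version is described.

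Section 8.3 then plans a multilevel analysis of the repeated measures "to analyze changes over time for the different patient reported outcomes, such as cancer worries, anxiety, and depression".

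Table V (section 12) has four parts: background, procedures, surveillance burden and cancer worries (part III), and the HADS (part IV). The one item in part III that asks directly about worry is "Did the cyst surveillance change the extent to which you worry about cancer".

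**The concern.** A model of change over time needs the same quantity measured at each occasion. For cancer worries the printed form offers only a question about change and attributes that change to surveillance. A newly diagnosed patient filling in the form at entry has had no surveillance to attribute anything to. At later visits the answer is a perceived change from an unstated starting point, which is not a level of worry.

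At stake is one of the three outcomes that section 8.3 names. The protocol sets the danger of a missed cancer against the harm of redundant investigation (section 1), and whether surveillance raises or lowers cancer worry bears on that balance. The gap cannot be closed at the analysis stage, because a level that was never asked cannot be recovered and an entry value cannot be collected afterwards.

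**Working it through.** No figure in the protocol bears on this point, so the check compares the schedule, the population and the planned analysis with the printed items.

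**1. Has surveillance begun at entry?** Section 5.1 treats a cyst as new if it was diagnosed less than 6 months before inclusion. Section 6.3 recommends follow-up at one-year intervals, or at 6 months in the first year for new cysts of 1 cm or more. On that schedule a newly diagnosed patient has had the diagnostic work-up at entry but no surveillance visit.

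**2. Which part III items can be answered at entry?** The classification below is a judgement from the printed wording; items are paraphrased.

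| Usable at entry? | Items | Count |
|---|---|---|
| No, presupposes surveillance undergone | check-ups a burden; nervous on attending; surveillance altered cancer worry | 3 |
| Only as an expectation | checking reduces fear; checking reassures; benefits exceed drawbacks | 3 |
| Yes | checking finds cancer early; checking may create uncertainty; checking is pointless; dread of the next visit; preferred frequency; preferred duration | 6 |

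Total: 3 + 3 + 6 = 12. Items giving a current level of cancer worry: 0 of 12. The item on reduced fear is an opinion about what checking does and does not report how much fear there is.

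**3. What do the other parts supply?** Part II covers imaging burden. It can be scored at entry for the work-up, since section 5.1 says "A high quality cross-sectional imaging study, either Computed Tomography (CT) or Magnetic Resonance Imaging (MRCP) should always be performed". Part IV, the HADS, has 14 items on present feelings, so anxiety and depression have an entry value and comparable later values. It does not ask about cancer, and section 8.3 lists cancer worries separately from both.

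**4. Can the change item serve as a repeated measure after entry?** Suppose worry rises by d at the first visit and stays there. The result over three visits depends on what patients compare with:

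- With the time before surveillance: answers d, d, d. Mean = d; slope = 0.
- With the previous visit: answers d, 0, 0. Mean = d/3. With visits coded −1, 0, 1, slope = (−1·d + 0·0 + 1·0) / (1 + 0 + 1) = −d/2 per visit, although worry never fell.

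The true course after the first visit is flat at d above entry. One history thus gives two different means and two different slopes, and the form does not say which comparison applies. This illustrates the ambiguity and does not predict how patients will answer.

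**The case against.** **The gap might be inferred to cover burden as a whole.** A reader might conclude that newly diagnosed patients cannot score the burden and worry items at entry, or that burden is first scorable after the first visit. The protocol does not support this. Only three of the 12 items presuppose surveillance, and imaging burden is scorable from the work-up. Burden of check-ups also has no natural level before a check-up, so a missing entry value there is not a design error.

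**The change item might be thought to hide a rise in worry.** A zero slope could be taken to mean that an increase goes unseen. That does not follow. If patients compare with the time before surveillance, the mean answer still shows d, and section 8.1 promises descriptive results for secondary endpoints. What stands is that the reference point is unstated, so neither the mean nor the slope has a fixed meaning.

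**No contrast with entry is promised.** Section 8.3 speaks of change over time, and the choice of model reference belongs in a statistical analysis plan, which is not shown. This is fair for the choice of contrast. It does not help with content: without a level item, no choice of reference yields a trajectory of cancer worry.

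**Table V may be abridged.** Parts I and II are topic lists, part II mentions worries in its title but prints only an imaging line, and no response options appear. A fuller form with a level item, or an entry version, could exist. This stands as a limit. It would be too strong to say that every questionnaire patient lacks an entry value; the supportable statement is that none is printed.

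**Conclusion.** The point holds in a limited form. As printed, Table V provides neither an entry value nor a repeated level for cancer worries, while section 8.3 names them for an analysis of change over time. This affects one of the three outcomes named there; the HADS serves the other two. Both primary endpoints are untouched, and so is the clinical outcome input to the MISCAN model.

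The conclusion rests on three assumptions: that Table V shows all the cancer-worry content of the questionnaire, that the same form is used at entry and later, and that newly diagnosed patients have had no surveillance visit before inclusion. If the full instrument already has a current-level item, the point reduces to printing it in Table V.

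The change is worth making because the repair is cheap and the missing values cannot be obtained later.

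**What to change.** - **Add a level measure.** Put a short current-level cancer-worry item or scale with a fixed recall window into Table V part III, for example how often the patient worried about getting cancer in the past month, on a 4-point scale. Word it identically at entry and at every later questionnaire.
- **Use it in section 8.3.** Name this measure and the HADS as the outcomes of the change-over-time model.
- **Move three items.** Ask about check-ups being a burden, nervousness on attending, and surveillance having changed worry only from the first post-visit questionnaire. Report the change item descriptively.
- **Patients already enrolled.** For those who entered without the new item, limit the change-from-entry analysis to the HADS.

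The cost is about one extra minute per form, an entry version of the form, and notification to the METC under section 10.2. The entry value of cancer worry is lost for patients already enrolled.
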